4.4.2.2 Global Outcome Measure

Global outcome measure is derived from mRS = 0 or 1, NIHSS = 0 or 1, BI \geq 95, and GOS = 1 at Day 90, considered as a whole. If death occurs prior to Day 90, all four binary outcomes will be considered as not being achieved in the analysis.

The NIHSS score is the total from scoring 11 items, assessed by a clinician. Items that are not applicable are not included in the total. It is not expected that any items will be applicable but missing; in such cases, the total score will be missing. The total score ranges from 0 to 42. NIHSS score will be collected pre-treatment, and then after 22-36 hours from start of study drug administration, after 5 days or at discharge from hospital, and at Day 90.

The Barthel index (BI) measures activities of daily living by having an assessor rate 10 items, with possible scores of 0, 5, 10 or 15. A total score, ranging from 0 to 100, is computed as the sum of the ratings from the 10 items. As this is a rater-completed assessment, no missing data are expected. However, if any item is not scored, then a score of 0 will be given as it will be presumed the subject did not meet the defined criteria for the item (20).

Glasgow Outcome Scale (GOS) is an evaluation of the outcome of stroke, assessed on a scale ranging from 1 to 5 by a clinician. The scale will be reversed from the

Statistical Analysis Plan: Alteplase—Genentech USMA
16/ML29093 5/17/2017

original published version (7) to assign lower scores to more favorable outcomes. The score is collected once in the study at Day 90.

The observed proportion of patients with a favorable outcome within each treatment group will be provided for the NIHSS (=0 or 1), BI (≥ 95) and GOS (=1) components of the global outcome measure, in a similar fashion as described for the primary outcome.

Treatment comparisons will be performed considering the four binary outcome measures as 4 dimensions of the outcome endpoint (12). These dimensions will be assumed to have a common odds ratio adjusted for pre-treatment NIHSS score, age, and last known well time to treatment. Quadratic terms for the continuous covariates may be added to the model, if the Wald p-value for the quadratic term is < 0.1 . No interactions among the covariates will be included in this model. Estimation will be performed using generalized estimating equations for a logistic model with correlation between the four outcomes of the same patient. Details of this model can be found in Appendix D. The estimated common odds ratio and its two-sided 95% CI will be reported.

Each individual outcome measure will be evaluated separately: odds ratios with two-sided 95% CIs will be derived from a logistic model with the same covariates as used for the global outcome measure to facilitate interpretation of the results.

LOCF and hot deck imputation will be used for the missing mRS component, similarly to the primary analysis. No imputation is planned for the other missing components, other than the non-achievement imputation in the event of death. However, incomplete component sets can still contribute to the model and will be included.

4.4.3 Exploratory Efficacy Endpoints

4.4.3.1 Exploratory Analyses for the Primary Endpoint

The primary analysis of the mRS 0-1 outcome will be complemented with exploratory supportive evaluations of treatment group differences.

The following analyses will be conducted to construct risk differences for mRS 0-1. Missing values for day 90 mRS will be imputed in the same manner as for the primary efficacy analysis unless otherwise specified.

Statistical Analysis Plan: Alteplase—Genentech USMA
17/ML29093 5/17/2017

- Unadjusted risk difference.
- Adjusted risk difference, from a linear regression with treatment, age, onset time to treatment, baseline NIHSS, and propensity score as covariates. The propensity score is derived from a logistic regression for treatment group with imbalanced covariates included in the model as covariates. This analysis will be triggered by presence of baseline imbalance. The criteria for baseline imbalance and details of this model are described in [Appendix E](#).

The following analyses will be conducted to construct the odds ratio for mRS 0-1 such that the direction of the odds ratio reflects change in the likelihood of achieving a favorable outcome if treated with IV alteplase:

- Logistic regression, adjusting for pre-treatment NIHSS score, age, and last known well time to treatment as continuous covariates. Quadratic terms for the continuous covariates may be added to the model, if the Wald p-value for the quadratic term is <0.1. No interactions will be included in this model.
- Repeated measures model
mRS outcomes at Day 30 and Day 90 will be modeled jointly by a logistic regression, using the GEE approach to account for the correlation between Day 30 and Day 90 outcomes of the same subject. Detailed description of this model is provided in [Appendix D](#). No imputation will be performed for missing mRS for this particular analysis.

4.4.3.2 Additional Exploratory Analyses

To characterize treatment response among the subset of subjects with confirmed strokes, adjusted risk difference for the primary efficacy outcome will be repeated on the subset of patients with stroke mimics excluded. In addition, analyses as specified in section [4.4.2](#) for the secondary efficacy outcome measures will be produced for confirmed strokes.

4.4.3.3 Modified Rankin Scale

The mRS score will be used to evaluate the proportion of patients with a score = 0 vs 1 or higher. Observed percentages and adjusted risk difference will be presented. The adjustment will be performed in the same way as for the primary endpoint. Adjusted odds ratio will be presented in a separate analysis for this outcome in the same fashion as for mRS 0-1.

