4.3 ANALYSIS OF TREATMENT GROUP COMPARABILITY

Clinically important demographic and disease characteristics at screening will be summarized overall and for each treatment group. Summaries will be produced for the ITT population.

Statistical Analysis Plan: Alteplase—Genentech USMA
12/ML29093 5/17/2017

Continuous variables will be summarized among patients with non-missing values, by the mean, standard deviation, median, first and third quartiles, minimum and maximum values. The number of patients with non-missing values will be displayed as well. Categorical variables will be summarized using numbers and percentages of patients in each category; unknown or missing will be included as a separate category.

The variables to be summarized include but are not restricted to the following:

- Demographics: sex, ethnicity, race(s), age (continuous and categorized as < 65 vs. ≥65)
- Last known well time to treatment (continuous and categorized as 0-2 hours, > 2-3 hours and >3 hours)
- Stroke characteristics: previous stroke (Y/N), RISS or non-RISS, stroke etiology, location of stroke
- NIHSS: total score (as continuous and categorical)
- Baseline substance use status: smoking and drug/substance abuse
- Medical History (MedDRA), in particular hypertension, diabetes mellitus, atrial fibrillation, and prior stroke
- Baseline Vital Signs: systolic and diastolic blood pressure and pulse
- Use of Aspirin / antiplatelet drugs within 7 days prior to screening/stroke onset
- Use of Heparin / anticoagulant drugs within 7 days prior to screening/stroke onset
- Prior medications
- Baseline neuroimaging (central reading)
- Baseline Lab Parameters: hematology (complete blood count without differential), chemistry (serum glucose), coagulation (international normalized ratio, partial thromboplastin time)

Baseline for NIHSS, vital signs and lab parameters will be defined as the last available assessment prior to initiation of any study medication.

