4.4.1 Primary Efficacy Endpoint

The primary efficacy analysis will estimate the effect of treatment with IV alteplase therapy and with the standard medical care (aspirin) in AIS patients with mild symptoms. The primary efficacy outcome is derived from the mRS.

The mRS is an assessment of disability with values from 0 (no symptoms at all) to 5 (severe disability); death will be scored as a '6'. The mRS is collected at 30 and 90 days after start of study drug administration. If death occurs prior to an assessment day (Day 30 or Day 90), the mRS will be considered available and will be set to 6.

The proportion of patients within each treatment group with a favorable outcome, defined by mRS of 0 or 1 at 90 days post-randomization, will be estimated in the IV alteplase arm and in the standard medical care arm. Reasons for not performing the assessment of mRS at Day 90 will be summarized.

The difference in proportions between the two groups will be estimated using the risk difference. The risk difference will be obtained from a linear model with the binary mRS 0-1 outcome as the response, treatment, and age, time from last known well to treatment, and baseline NIHSS as continuous covariates. Quadratic terms for the continuous covariates may be added to the model, if the Wald p-value for the quadratic term is <0.1. No interactions among the covariates will be included in this model.

A common approach for implementation of this model is binary regression, a GLM with the Bernoulli distribution for the outcome and the identity link function. This

Statistical Analysis Plan: Alteplase—Genentech USMA
14/ML29093 5/17/2017

model has a possibility of non-convergence when the estimated response probability falls outside of the (0,1) interval. To circumvent the non-convergence problem, an approach of using the ordinary least squares with a robust standard error is used in this study. It was shown that if a robust standard error is used with the ordinary least squares estimation, the estimate of the risk difference is equal or similar to the estimate from the GLM with an identity link for Bernoulli outcome approach (22, 23).

The primary efficacy analysis will include all ITT patients, with patients grouped according to the treatment assigned at randomization. Missing or out of window mRS at Day 90 will be imputed with LOCF or late Day 90 mRS, if available, or simulated with a hot deck method (see Section 4.7 for handling of missing mRS).

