4.4.2.1 Ordinal Modified Rankin Scale

As a secondary endpoint, mRS at Day 90 will be further explored on the range of the values (0 to 6) where the values of 5 and 6 are grouped. The distribution of full range of mRS scores at Day 90 (imputed) will be summarized by treatment group. Both tabular displays and stacked bar charts will be prepared.

Statistical Analysis Plan: Alteplase—Genentech USMA
15/ML29093 5/17/2017

The comparison will be achieved by fitting a proportional odds model with mRS score at Day 90 as the dependent variable, and treatment group, pre-treatment NIHSS score, age, and last known well time to treatment as the continuous predictors (1, 8). Quadratic terms for the continuous covariates may be added to the model, if the Wald p-value for the quadratic term is <0.1 . No interactions among the covariates will be included in this model. The adjusted odds ratio with its two-sided 95% CI will be shown. Direction of the odds ratio will be chosen to reflect change in the odds of achieving a lower (better) mRS if treated with IV alteplase.

The proportional odds assumption will be tested by the score test, and the p-value will be reported. If the proportional odds assumption does not hold, the resulting odds ratio will not be presented. The alternative analysis planned for this situation will provide the adjusted mean difference between mRS scores with two-sided 95% CI. Methodology for this estimation is similar to the primary outcome, but using the ordinal mRS as the dependent variable.

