Signed informed consent prior to initiation of any study-specific procedure or treatment. The patient or the patient's legally authorized representative must be able to provide written informed consent and understand the potential risks and benefits from study enrollment and treatment.

Exclusion Criteria

Patients who meet any of the following criteria will be excluded from study entry:

Computed tomography (CT) or magnetic resonance imaging (MRI) findings consisting of one of the following:

- CT with clear large hypodensity that is greater than one-third middle cerebral artery (MCA) territory (or greater than 100 cc if not in MCA territory),
- MRI with clear large hyperintensity on concurrent diffusion-weighted (DW) and fluid-attenuated inversion recovery (FLAIR) that is greater than one-third MCA territory (or greater than 100 cc if not in MCA territory),
- Imaging lesion consistent with acute hemorrhage of any degree, OR
- Evidence of intraparenchymal tumor

Disability prior to the presenting stroke (historical mRS score ≥ 2)

Standard contraindications to IV alteplase for patients treated within 3 hours of symptom onset, including:

- Head trauma or previous stroke within the previous 3 months
- Myocardial infarction within the previous 3 months
- Gastrointestinal or urinary tract hemorrhage within the previous 21 days
- Major surgery within the previous 14 days
- Arterial puncture at a non-compressible site within the previous 7 days
- Any history of ICH with the exception of < 5 chronic microbleeds on MRI
- Elevated blood pressure (systolic > 185 mm Hg or diastolic > 110 mm Hg), or the use of aggressive measures (use of more than two intravenous agents to lower blood pressure) to achieve blood pressure within acceptable parameters
- Treatment with unfractionated heparin within the last 48 hours and activated partial thromboplastin time outside of the normal range as specified by the center's local laboratory
- Blood glucose < 50 mg/dL
- International normalized ratio > 1.7 (Note: This does not need to be verified prior to randomization if there is no clinical suspicion of abnormality.)
- Platelet count of $< 100,000/\text{mm}^3$ (Note: This does not need to be verified prior to randomization if there is no clinical suspicion of abnormality.)
- Treatment with a direct thrombin inhibitor or factor Xa inhibitor (including novel oral anticoagulants [e.g., dabigatran, rivaroxaban, apixaban, edoxaban]) within the last 48 hours

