of missing values in a categorical variable, missing may be considered as a standalone category for the purpose of generating a propensity score.

Table 6
Baseline Characteristics to be Evaluated for Imbalance

Sex	Prior anti-platelet drug use
Race	Prior anti-coagulant drug use
Ethnicity	Baseline glucose
Smoking	Baseline systolic blood pressure
Medical History	Baseline coagulation test: INR
- Hypertension	
- Diabetes Mellitus	
- Atrial Fibrillation	
- Stroke	

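### Pre-stroke mRS (0 or 1) is left out of the mRS 0 and ordinal mRS models: avoidable imprecision, chiefly for the exploratory mRS 0 risk difference, but no bias

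*SAP*

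**What the plan says.** **Who enters.** The exclusion criteria (SAP Appendix A) list "Disability prior to the presenting stroke (historical mRS score ≥ 2". Patients with pre-stroke mRS 0 and patients with pre-stroke mRS 1 are therefore both eligible.

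**What is analysed.** Section 4.4.1 describes the scale: "The mRS is an assessment of disability with values from 0 (no symptoms at all) to 5 (severe disability". Section 4.4.3.3 states: "The mRS score will be used to evaluate the proportion of patients with a score = 0 vs 1 or higher". The same cut applies to every patient. Section 4.4.2.1 analyses the ordered scale, with 5 and 6 grouped, as a secondary endpoint.

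**What is adjusted for.** The primary linear model contains "treatment, and age, time from last known well to treatment, and baseline NIHSS as continuous covariates". For mRS 0, "The adjustment will be performed in the same way as for the primary endpoint", and the odds ratio follows the logistic analysis of mRS 0–1, which has the same three covariates. The ordinal model has "treatment group, pre-treatment NIHSS score, age, and last known well time to treatment as the continuous predictors".

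**Where else pre-stroke mRS might appear.** It is not among the 13 items of Table 6 ("Baseline Characteristics to be Evaluated for Imbalance") or the four subgroup variables of section 4.4.4. Section 4.3 does not name it either, but that list is open: "The variables to be summarized include but are not restricted to the following".

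**The concern.** Pre-stroke mRS is a baseline value on the outcome's own scale. A patient who enters at mRS 1 and returns exactly to that state scores 1 at Day 90, which is a non-response on mRS 0 and one category below the best on the ordinal scale. One would therefore expect pre-stroke mRS to predict both outcomes, and mRS 0 most directly. Leaving it out of the models forgoes precision and leaves any chance imbalance between arms unadjusted.

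This matters somewhat more here than usual. Enrollment stopped at 313 of a planned 948, section 2.3 concedes that the study is substantially underpowered, and every efficacy result is now an estimate with a confidence interval. Baseline adjustment is one of the few means left of narrowing those intervals.

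**Working it through.** **Plan's own figures.** No figure in the SAP bears directly on this point. Table 1 does give the overall control rate for mRS 0–1: 0.9 × 0.74 + 0.1 × 0.80 = 0.746. With 145 per arm, one-sided alpha 0.025 and the effect diluted by 0.9 × 0.99, power comes to 24.6%, 31.1% and 38.4%, against the stated 25%, 31% and 38%. Table 1 reproduces and is not in question. It supports a rate of about 0.75 for mRS 0–1 below.

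**Inputs**

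| Input | Value | Source |
|---|---|---|
| N randomized | 313 | SAP 2.3 |
| Overall mRS 0–1 rate, p | 0.75 | rounded from Table 1 assumptions |
| Overall mRS 0 rate, p | 0.45 | assumed |
| Share with pre-stroke mRS 1, q | 0.10 to 0.30 | assumed |
| Gap in mRS 0 rate, d | 0.35 to 0.50 | assumed |
| Gap in mRS 0–1 rate, d | 0.10 to 0.20 | assumed |

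**Formulas** (linear risk-difference model, two equal arms)

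- Variance explained: R² = q(1−q)d² / [p(1−p)]
- Reduction in SE: 1 − √(1−R²)
- SD of the chance shift in the risk difference: d × √(4q(1−q)/N)
- Unadjusted SE: √(4p(1−p)/N)

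**mRS 0.** The unadjusted SE is √(4 × 0.2475/313) = 0.0562, so the 95% half-width is 1.96 × 5.62 = 11.0 points.

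- Low end (q = 0.10, d = 0.35): R² = 0.09 × 0.1225/0.2475 = 0.045. SE reduction is 1 − √0.955 = 2.3%. Chance shift is 0.35 × √(0.36/313) = 0.35 × 0.0339 = 1.2 points.
- High end (q = 0.30, d = 0.50): R² = 0.21 × 0.25/0.2475 = 0.212. SE reduction is 1 − √0.788 = 11.2%. Chance shift is 0.50 × √(0.84/313) = 0.50 × 0.0518 = 2.6 points.

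The half-width would fall from 11.0 points to between 10.8 and 9.8.

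The shift and the SE reduction are one loss shown in two ways: (1.19/5.62)² = 0.045 and (2.59/5.62)² = 0.212, which are the two R² values. They must not be added together.

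**mRS 0–1 (primary).** The unadjusted SE is √(4 × 0.1875/313) = 0.0490.

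- Low end (q = 0.10, d = 0.10): R² = 0.09 × 0.01/0.1875 = 0.0048. SE reduction is 0.2%, shift 0.3 points.
- High end (q = 0.30, d = 0.20): R² = 0.21 × 0.04/0.1875 = 0.045. SE reduction is 2.3%, shift 1.0 point.

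**Check with a different set-up.** Take 5–30% with pre-stroke mRS 1, a 0–10% chance of mRS 0 in that group in both arms, a 45% control rate in the others and a 9-point difference among them. The SE reduction is then 1.5–12% and the shift 1.0–2.6 points, against an SE of 5.4–5.6 points. The order of size is the same.

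**Limits of the arithmetic.** R² is marginal. Age and NIHSS are already in the model and may carry part of the same information, so the incremental gain is smaller to that extent. The formulas hold for the linear risk difference only. In a logistic or proportional odds model, a prognostic covariate changes the odds ratio to one conditional on that covariate, and the SE of its logarithm generally does not fall. No precision figure is therefore given for the odds-ratio analyses.

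**The case against.** The strongest reply is that three prespecified covariates, which match the synopsis stratification factors and the hot-deck cells, are a coherent choice. Omitting a fourth prognostic variable from a randomized comparison is not an error. This stands as far as bias goes: the plan's estimates are valid, and their intervals already include the chance imbalance.

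The second reply is that the value may not exist. Applying the criterion needs only a yes or no on mRS 2 or more. The schedule in Appendix B lists mRS only at Days 30 and 90, and its footnote on medical history mentions smoking and stroke history. The SAP dates from May 2017, after enrollment ended in December 2016, so a missing field can no longer be collected prospectively. This stands too and makes the fix conditional.

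Three stronger readings are tempting, and the SAP does not support them:

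- *A reader might infer that full recovery is wrongly counted as failure and that adjustment cures this.* The SAP describes mRS 0 as absence of symptoms and does not present it as return to the pre-stroke state. A covariate leaves the scoring unchanged. If patients entering at mRS 1 could not benefit on this endpoint, a 9-point difference among the others would average 9 × 0.90 = 8.1 to 9 × 0.70 = 6.3 points overall. That is a property of the endpoint in the enrolled population, and a main-effect covariate does not undo it. The primary endpoint already counts a return to mRS 1 as favorable.
- *A reader might infer that an imbalance would go unseen.* The section 4.3 list is expressly not exhaustive, so this is not established.
- *A reader might look to Table 6 for the remedy.* The propensity score analysis it feeds is specified only for mRS 0–1, so an entry there would do nothing for mRS 0 or ordinal mRS.

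**Conclusion.** The point holds as a minor, optional improvement. Pre-stroke mRS 0 and 1 are both admitted, and neither the mRS 0 nor the ordinal mRS model uses the distinction. There is no systematic bias between arms.

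The loss is at most about 2–11% of the SE of the exploratory mRS 0 risk difference, given an assumed 10–30% prevalence, a 35–50 point gap and a 45% overall rate, none of which the SAP supplies. It is less to the extent that age and NIHSS already carry the information. For the primary analysis it is about 0.2–2% and can be ignored. For the secondary ordinal model, the case rests on conditioning on a likely prognostic baseline value and addressing chance imbalance in it, with no claim of a smaller SE. Confidence in the size is low, because everything depends on the unknown share entering at mRS 1.

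**What to change.** First confirm that the case report form holds historical mRS as a value, 0 versus 1, and not only as a yes/no eligibility answer. If it does, amend the SAP before unblinding:

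1. Sections 4.4.3.3 and 4.4.2.1: add pre-stroke mRS (0 versus 1) as a binary covariate in the mRS 0 risk-difference model, the mRS 0 odds-ratio model and the ordinal mRS model. State that the odds ratios are conditional on it.
2. Section 4.3: name it as a baseline variable to be shown by arm.
3. Leave the primary model as it is.

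The cost is a few lines of SAP text, one more model term and one baseline-table row. If the 0/1 value was not recorded, no change is possible and the point lapses.

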4.4.3.4 National Institutes of Health Stroke Scale

Descriptive statistics (n, mean, standard deviation, median, quartiles, minimum, and maximum) will be provided for NIHSS score by treatment group, both at Day 5 / Hospital discharge and at Day 90. Reasons for not performing the assessment of NIHSS at Day 90 will be summarized.

The NIHSS score will be used to evaluate the proportion of patients with a score = 0 vs 1 or higher, and separately, 0-1 vs. 2 or higher. Observed percentages and adjusted risk difference will be presented. The adjustment will be performed in the same way as for the primary endpoint. Adjusted odds ratio will be presented in a separate analysis for this outcome in the same fashion as for mRS 0-1.

